7.2 Safety monitoring

7.2.1 Safety monitoring for QT prolongation in Phase 2

In March 2022, a training on QT measurement and interpretation on 12-lead ECG and the Kardia 6L will be given to the study team by a referent cardiologist with extensive experience in the use of bedaquiline for tuberculosis treatment, the cardiologist at a specialist cardiology service, and the study investigator. Both dedicated 12 lead ECG instruments with electronic and paper data capture will be used as well as the Kardia app (Alivecor), which was FDA approved for the diagnosis of atrial fibrillation, and has been validated against 12-lead ECG based QTc measurements with a good correlation. [39] The measured QT will be corrected by the Fridericia formula through a dedicated calculator.

In the phase 2 study planned for July 2022, participants will have their QTc interval screened at baseline (within 1 week before PEP administration) by the Kardia app and a 12-lead ECG (reference standard) to validate the accuracy of the Kardia app in this specific setting. If QTc \geq 450ms is confirmed by qualified readers, the participant will be excluded from the Phase 2 safety study. If the QTc by 12 lead ECG is found to be <450 ms, the participant is not excluded. All ECGs will be time stamped and stored as pdf in the RedCap database for blinded review by a referent qualified reader based at the department of Cardiology of the Amsterdam University Medical Center location AMC.

Those participants with QTc <450 ms, and whose baseline ALT is <3 x ULN, will receive study treatment if eligible. QTc will be measured 24 hours later, and ALT 14 days after administration.

If after single dose administration of bedaquiline and/or rifampicin, and in the unexpected event that QTc prolongation >60 ms since baseline or a value of >500 ms is seen, the participant will be urgently brought to the cardiology service at a specialist cardiology service for further examination, continuous rhythm monitoring, repeated QTc measurements, and measurement of potassium for correction of hypokalemia. The ECG will be reviewed for additional warning signs of impending malignant

dysrhythmias and IV magnesium and isoprenaline may be administered, per the cardiologist's management. These procedures will be described in a separate cardiology monitoring SOP.

7.2.2 Safety monitoring for hepatitis in Phase 2

For laboratory measurements see section 5.2.1. In case of ALT or AST values of $>3x$ ULN at baseline, participants will not be eligible for study medication. In case of ALT/AST elevations $>3x$ ULN after study medication, participants will undergo further ALT/AST monitoring with frequency and need for referral depending on the level of elevation.

7.2.3 (S)AE monitoring

The occurrence of any adverse events (AE) will be assessed the day after administration. An AE is any untoward medical occurrence in a clinical investigation subject administered a pharmaceutical product and which does not necessarily have a causal relationship with this product. It can be any unfavorable and unintended sign, symptom, or disease temporally associated with the use of a medicinal (investigational) product, whether or not related to this product. Participants who receive PEP will be instructed to inform the study staff of any adverse events occurring between the administration of the drug and 30 days after. All relevant study staff will be trained on (S)AE detection, (S)AE monitoring mechanisms and (S)AE reporting on site. During the training, examples of (S)AE reporting cases will be given. SAE checklists and forms will be explained as well.

In the Phase 2 study, a physician from the study team will be available in the village and a cardiologist will be on call at a nearby specialist cardiology service. In the Phase 3 study, the participants are encouraged to contact the study staff while the study teams are still in the village, or afterwards a community health officer or by using the contact details in the information form of which each household will receive a copy. For all participants provided study medication, study teams will- on arrival in the village the next day- start by visiting their houses to verify for any (S)AEs. In case the participant is not at home, another attempt will be made within the next 3 days.

For phase 2 the medical staff will specifically enquire about gastro-intestinal (nausea, vomiting, diarrhea), nervous system-related (headache, dizziness), cardiac symptoms (syncope) and cutaneous reactions. These reported adverse events will be recorded, together with their severity and relatedness to the study medication.

During phase 3, active adverse event monitoring will take place during the safety follow-up visit after PEP intake. All participants that took PEP will be revisited and will be asked if they experienced any adverse events. The participants absent during the 1st safety follow-up visit will be revisited one additional time. Further participants that took PEP and the community health officer (agent de santé Communautaire) present during PEP intake will be sensitized on reporting/being vigilant of adverse event appearing after the safety follow-up visit or pregnancies within 30 days of the PEP intake. They will be informed that in this case they will need to reach out to the study team that will be responsible for follow-up and reporting of the respective event. These will be considered spontaneously reported adverse events.

Medical staff in health facilities in the districts concerned will also be informed about the trial in advance (and at the beginning of every yearly screening round) and will be asked to report any possible adverse reactions (AR) or serious adverse event (SAE) to the study team. An AR is an AE for which there is at least a reasonable possibility that it might be linked to the medicinal product under study. A SAE is an AE that 1) results in death, 2) is life-threatening, 3) requires inpatient hospitalization or prolongation of existing hospitalization, 4) results in persistent or significant disability/incapacity, or 5)

is a congenital anomaly/birth defect. ARs will be reported in the same manner as AEs. In case of a SAE however, the SAE report template will be completed by the study team and sent to the sponsor ([contact]) within 24 hours following the notification of the SAE to the study team as per the SAE reporting instructions.

Only events (AE, AR, SAE and pregnancies) that occur between the administration of the drug and 30 days after will be recorded for study purposes. Any additional safety information obtained until 30 days after each dose of the Janssen Product(s) Under Study will be reported to Janssen Pharmaceutica NV. All subsequent AEs, ARs and SAEs spontaneously reported beyond 30 days after each dose of the Janssen Product(s) under study shall be collected/reported if the investigator considers the event to be causally related to the use of the Janssen Product(s) under study.

All SAE's whether or not deemed drug related or expected must be reported immediately or within 24 hours (one working day) using the SAE Notification Form by email to:

Clinical Trials Unit
Institute of Tropical Medicine
[name]
[name] – Belgium
Email: [contact]

Line listings of all reported SAE's will be sent to the IRB of the ITM and the independent EC, on a yearly basis. A study safety checklist SOP will be prepared describing all responsibilities and actions that are required in case of an SAE.

For phase 2, concomitant medication will be recorded in the REDCap study database and as explained in section 4.2 above, a safe list will be provided that contains all essential medications registered in Comoros that are not considered a risk when administering BE-PEP. For any medication encountered that is not on this safe list and that is also not on the list of forbidden medications, the field teams will consult the local PI and an expert on the matter ([name] and [name]) to decide whether it will be added either to the safe list or to the list of forbidden medication.

As part of the baseline survey in the new villages of BE-PEOPLE that were not part of the PEOPLE trial, we will collect information on medications used to allow us to update the safe list ahead of the start of the phase 3 intervention in 2023. During phase 3, this list will be used to determine PEP eligibility on an individual level (see inclusion/exclusion criteria). Participants will be excluded from Bedaquiline when they take a medication not included on the safe list. This medication will be reported. Concomitant medication included on the safelist will not be reported. Throughout the phase 3 trial, the safe list may be periodically updated based on the exclusion data captured in REDCap.

For BE-PEOPLE, an independent Data Safety Monitoring Board (DSMB) will review the (S)AEs and outcome of the Phase 2 study, with pre-specified criteria on stopping (see section 8) versus continuing in the Phase 3 study. During the phase 3 study the DSMB will also review active (S)AE follow-up.

NOTE (1): In general, hospitalization signifies that the participant has been detained (usually involving at least an overnight stay) at the hospital or emergency ward for observation and/or treatment that would not have been appropriate in the physician's office or out-patient setting. Complications that occur during hospitalization are AEs. If a complication prolongs hospitalization or fulfils any other serious criteria, the event is an SAE. When in doubt as to whether "hospitalization" occurred or was necessary, the event should be considered an SAE. Hospitalization for elective treatment of a pre-existing condition that did not worsen from baseline is not considered an SAE, nor hospitalization for non-medical reasons (e.g., the participant stays at the hospital overnight because (s)he lives too far and/or there is not transport).

NOTE (2): The term disability means a substantial disruption of a person's ability to conduct normal life functions. This definition is not intended to include experiences of relatively minor medical significance such as uncomplicated headache, nausea, vomiting, diarrhea, influenza, and accidental trauma (e.g. sprained ankle) which may interfere or prevent everyday life functions but do not constitute a substantial disruption.

NOTE (3): The term 'life-threatening' in the definition of 'serious' refers to an event in which the subject was at risk of death at the time of the event. It does not refer to an event, which hypothetically might have caused death, if it were more severe.

All SAEs must be:

- recorded on the appropriate SAE report form
- followed through resolution by a study clinician
- reviewed and evaluated by a study clinician.
- Follow-up until resolution (by sending updates on the SAE form)

Severity, relationship of event to study drug and outcome

All (S)AE's (phase 2 and phase 3) will be assessed by the clinician (obligatory for SAE's) or study nurse using a predefined grading system:

1. **Mild:** events require minimal or no treatment and do not interfere with the participant's daily activities.
2. **Moderate:** events result in a low level of inconvenience or concern with the therapeutic measures. Moderate events may cause some interference with functioning.
3. **Severe:** events interrupt a participant's usual daily activity and may require systemic drug therapy or other treatment. Severe events are usually incapacitating.
4. **Life-threatening:** Participant at risk for death at the time of the event

Changes in the severity of an (S)AE will be documented to allow an assessment of the duration of the event at each level of intensity to be performed. Adverse events characterized as intermittent require documentation of onset and duration of each episode.

Assessment of causality

The investigator or study nurse is obliged to assess the relationship between investigational product and the occurrence of each (S)AE. The investigator (for AE's and SAE's) or study nurse (for AE's) will use clinical judgement to determine the relationship. Alternative causes, such as natural history of the underlying diseases, concomitant therapy, other risk factors, and the temporal relationship of the event to the IMP will be considered and investigated. The investigator will also consult the drug information and the DSMB as needed in the determination of his/her assessment.

For phase 2, the relationship of an adverse event to study drug is to be assessed according to the following definitions and can only be done by the study physician:

1. **Definitely unrelated:** Reserved for those events which cannot be even remotely related to study participation (e.g. injury caused by a third party).
2. **Unlikely:** There is no reasonable temporal association between the study drug and the AE and the event could have been produced by the participant's clinical state or other modes of therapy administered to the participant.
3. **Possible:** The suspected AE may or may not follow a reasonable temporal sequence from study drug administration but seems to be the type of reaction that cannot be dismissed as unlikely. The event could have been produced or mimicked by the participant's clinical state or by other modes of therapy concomitantly administered to the participant.
4. **Likely:** The suspected adverse event follows a reasonable temporal sequence from study drug administration, abates upon discontinuation of the drug, and cannot be reasonably explained by the known characteristics of the participant's clinical state.
5. **Definitely related:** Reserved for those events which have no uncertainty in their relationship to test drug administration: this means that a re-challenge was positive.

For phase 3, the relationship of an adverse event to study drug is to be assessed according to the following definitions:

1. **Possibly related:** Any AE with a potential link to PEP. Any AE presenting within 24 hours of PEP administration will be considered related to PEP if it is listed below:

Nausea	Syncope	Headache
Palpitation	Diarrhea	Dizziness
Vomiting	Skin reactions	

Other AEs occurring within 24 hours after PEP administration or AEs presenting after 24 hours will need to be evaluated on a case-by-case basis.

2. **Not related:** Any AE that is unrelated to the use of PEP OR the AE is related to the participant's medical condition or other treatment unrelated to the study.

For each SAE the outcome must also be assessed according to the following classification:

Recovered: The participant recovered from the event with no residual problems.

Not yet recovered: This outcome can only be used for Serious Adverse Events. The event no longer meets a 'Serious' criterion, but medical event is not yet completely cured. The remaining event should be listed as a separate adverse event in the adverse event table, and with its own outcome.

Permanent damage: The event has resulted in permanent impairment.

Ongoing: the participant is continued to be followed for the event.

Death: The participant died. This term should only be used for the event which resulted in death. Any other events which were present at the time of death, but were not the cause of death, should be listed as 'Ongoing'.

Unknown: The participant cannot be traced and no final outcome for the event could be determined.

There may be situations when an SAE has occurred, and the investigator has minimal information to include in the initial report to the Sponsor. However, it is very important that the investigator always makes an assessment of causality for every event prior to transmission of the report to the Sponsor. The investigator may change his/her opinion of causality in light of follow-up information, amending the SAE-report form accordingly.

7.2.4 Special Reporting Situation

All special reporting situations must be reported within 3 business days using the SAE or pregnancy form by email to:

Clinical Trials Unit
Institute of Tropical Medicine
[name]
[name] – Belgium
Email: [contact]

A study safety checklist SOP will be prepared describing all responsibilities and actions that are required in case of a special reporting situation.

An overview of all special reporting situations:

- Drug exposure during pregnancy (paternal, maternal)
- Suspected transmission of any infectious agent via administration of a drug under study.
- Overdose of a drug(s) under study*
- Exposure to a drug(s) under study from breastfeeding*
- Suspected abuse/misuse of a study product(s) under study*
- Inadvertent or accidental exposure to a study Product(s) under study*
- Any failure of expected pharmacological action (i.e., lack of effect) of a study Product(s) under study *
- Medication error (includes potential, intercepted or actual) involving a study product (with or without patient exposure to the Janssen Product(s) under study, e.g., name confusion)*
- Unexpected therapeutic or clinical benefit from use of a study Product(s) under study*

*** These special reporting situations only need to be reported to Janssen within 3 business days if the event is associated with an SAE. If the event is not associated with an SAE, the SS should be recorded in the CRF and sent annually to Janssen.**

7.2.5 Product Quality Complaints (PQC)

All PQC's must be reported within 3 business days using the PQC Notification Form by email to:

Clinical Trials Unit
Institute of Tropical Medicine
[name]
[name] – Belgium
Email: [contact]

Any complaint that indicates a potential quality issue during manufacturing, packaging, release testing, stability monitoring, dose preparation, storage or distribution of the product or delivery system is considered a PQC. Not all PQCs involve a patient.

A study safety checklist SOP will be prepared describing all responsibilities and actions that are required in case of an PQC.

Examples of PQC include but are not limited to:

- Mislabelling or misbranding

- Information concerning microbial contamination, including a suspected transmission of any infectious agent by a product
- Any significant chemical, physical, or other changes that indicate deterioration in the distributed product
- Any foreign matter reported to be in the product
- Mixed product, e.g., two drugs are mixed-up in the packaging process
- Incorrect tablet sequence (e.g., oral contraceptive tablets)
- Insecure closure with serious medical consequences, e.g., cytotoxics, child-resistant containers, potent drugs
- Suspected counterfeit or tampered product
- Adverse Device Effects including any adverse event resulting from insufficiencies or inadequacies in the instructions for use, the deployment, implantation, installation, operation, or any malfunction of a medical device or combination product. This also includes any event that is a result of a use error or intentional misuse and dosing device malfunctions (e.g., auto-injector button not working, needle detaching from syringe, etc.)
- Physical defect (e.g., abnormal product odour, broken or crushed tablets, etc.)

7.3 Surveillance for selection for mycobacterial drug resistance

The risk of inducing rifampicin resistance in (undiagnosed) tuberculosis or leprosy patients with one single dose of the drug is negligible.[40] As was described by Mitcheson for treatment of tuberculosis, resistance emerges as a result of selection of resistant mutants under conditions of monotherapy.[41] This requires high numbers of bacilli as observed in cavitary pulmonary tuberculosis, combined with prolonged exposure, as mycobacteria are slow to replicate. Repeated cycles of starting a treatment regimen, interrupting treatment, and restarting after some days can mimic monotherapy because of differential activity of drugs during the first days of treatment. However a single dose of rifampicin, possibly repeated once after four weeks, will not result in drug resistance. The BE-PEP regimen consists of two drugs, rifampicin and bedaquiline, further reducing the risk of selection of resistant mutants, although the half-life of bedaquiline and its metabolites far exceeds that of rifampicin.

To further decrease any potential risk of acquired drug resistance we will screen for signs and symptoms of pulmonary tuberculosis and exclude those participants from PEP.

We will also monitor molecular resistance for rifampicin and bedaquiline on samples from all leprosy patients, using an expanded Deeplex MycLep assay in which the *atpE* gene of *M. leprae* is included and using whole genome sequencing. Lastly, we will also recruit presumptive tuberculosis patients in Comoros for analysis of sputum and/or tongue swabs and genotype extracted *M. tuberculosis* DNA with the Deeplex MycTB XL, which includes additional targets potentially associated with bedaquiline resistance. Whole genome sequencing may be used to track the spread of drug resistant TB.

7.4 Other risks

Other risks to the participants are minimal. Leprosy patients identified will have a slit skin smear and a 4mm punch biopsy from the edge of the lesion taken (except if the lesion is in the face). The biopsy will be collected under local anesthesia. These procedures may cause slight pain, and carry a small risk of bleeding, which will be controlled by the person collecting these samples. The staff on the Comoros are already executing these procedures as part of the ongoing PEOPLE study.

8. STUDY MANAGEMENT

In the framework of the PEOPLE study, a bi-weekly meeting has been set-up for the purpose of the day-to-day management of the study and to discuss the progress of the trial. The meeting is attended by representatives of the sponsor and when required by representatives of the sites. These meetings will be continued within the BE-PEOPLE study (frequency will depend on study status). They will be organized by the clinical trials unit of ITM.

Also in the PEOPLE trial a Scientific Advisory Committee (SAC) has been established for the purpose of providing independent advice on the preliminary results that have been analyzed during the interim analyses. A charter detailing the modalities for this SAC has been drawn up. Members of the current SAC of the PEOPLE study will be asked to stay on as members of the SAC for BE-PEOPLE, if necessary additional members will be solicited. A new charter will be set-up and signed for BE-PEOPLE purposes.

For BE-PEOPLE, once Phase 2 study is finalized and after statical analysis is done, an independent Data Safety Monitoring Board (DSMB) will review the (S)AEs and outcomes of the Phase 2 study and advice on stopping versus proceeding to phase 3. The sample size chosen will allow for a precise estimate of the mean QTc and its variance. It will be left to the judgement of the DSMB whether any observed prolongation of QTc is clinically relevant and has implications for proceeding to Phase 3. Besides this, the Phase 2 study enrollment will be paused at any moment, if any of the below criteria is met.

1. Death of a participant considered related to study drug
2. One or more participants experience an SAE or Gr 4 AE or a persistent (upon repeat testing) Gr 4 laboratory abnormality that is determined to be related to study drug
3. Three or more participants experience a Gr 3 or greater AE of the same type (as per medical judgement) that is determined to be related to study drug
4. Three or more participants experience a persistent (upon repeat testing) Gr 3 laboratory abnormality related to the same laboratory parameter and considered to be related to study drug
5. Two or more participants experience QTc > 500 ms after intake of the study medication
6. One or more participants has AST or ALT > 8x ULN, in absence of causative explanation, after intake of the study medication

In this case a DSMB consultation will be held asap to discuss the further conduct of the trial. Enrollment and randomization should be paused until a DSMB decision is made, other follow-up visits can continue.

During the phase 3 study the DSMB will also review active (S)AE follow-up on the day after study medication administration.

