4.5.5 Termination of Study

The end of the study is defined as the date of the last visit (or last contact) of the last patient in the study.

If the study is prematurely terminated or suspended, the Sponsor will promptly inform the investigators/institutions, and the regulatory authority(ies) of the termination or suspension and the reason(s) for the termination or suspension. The ECs will also be informed promptly and provided the reason(s) for the termination or suspension by the Sponsor or by the investigator/institution, as specified by the applicable regulatory requirement(s).

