12.2 Protocol amendments

Once the final clinical study protocol has been issued and signed by the authorized signatories, it cannot be informally altered. Protocol amendments have the same legal status and must pass through the appropriate steps before being implemented. Any substantial change must be approved by all the bodies and EC's that have approved the initial protocol, prior to being implemented, unless it is due to participant's safety concerns (in which case the immediate implementation can be necessary for the sake of participant's protection. In case modifications to the protocol or amendment are requested by any local EC/CA during the review process, these must be discussed and agreed upon with the Sponsor prior to any resubmission incorporating those changes.

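### Section 8 limits every pause criterion to phase 2: no phase 3 event requires a pause, and events reported after the safety visit have no required DSMB review

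*Protocol*

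**What the plan says.** Protocol section 8 lists six criteria: a related death; a related SAE, Grade 4 event or persistent Grade 4 laboratory value; three related Grade 3 events of one type; three persistent related Grade 3 values of one parameter; two QTc values above 500 ms; and one unexplained AST or ALT above 8 times ULN. The lead-in is "Besides this, the Phase 2 study enrollment will be paused at any moment, if any of the below criteria is met". The next lines call for an urgent DSMB consultation and a halt to enrolment and randomization until the DSMB decides. SAP section 3.1.1 repeats the list, but that SAP covers phase 2 only.

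For phase 3, section 8 says: "During the phase 3 study the DSMB will also review active (S)AE follow-up on the day after study medication administration". Section 7.2.3 states the same role without naming a day. It places active monitoring at the safety visit, which Table 3 puts one day after each dose with a window of +3 days. Of events reported after that visit it says: "These will be considered spontaneously reported adverse events". The recording window is wider: "Only events (AE, AR, SAE and pregnancies) that occur between the administration of the drug and 30 days after will be recorded".

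Other provisions that bear on the point:
- Section 7.2.3 requires SAE reports to the sponsor within 24 hours. Under causality, it has the investigator consult the DSMB as needed, without limiting this to a phase or visit.
- Section 7.2.3, onward reporting: "Line listings of all reported SAE's will be sent to the IRB of the ITM and the independent EC, on a yearly basis".
- Section 7.2.3, a document not supplied: "A study safety checklist SOP will be prepared describing all responsibilities and actions that are required in case of an SAE".
- Section 4.5.5: "If the study is prematurely terminated or suspended, the Sponsor will promptly inform the investigators/institutions".
- Section 12.2 requires prior approval of substantial changes, "unless it is due to participant's safety concerns".
- Annex 1 (the Belgian regulator's advice, non-binding and given on an earlier protocol draft) asks for discontinuation and stopping criteria in phase 3 as well.

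**The concern.** Phase 3 is where a rare serious reaction would most likely first appear. It doses far more people, repeats BE-PEP after four weeks in household contacts, and includes children from age 5. It also drops safeguards that phase 2 had: Table 3 has no ECG or liver test, and the phase 3 eligibility lists in section 4.2 have no baseline QTc or ALT/AST exclusion. Clinical event reports are therefore the main safety signal.

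Two things follow if the protocol is applied as written. A death judged related to study drug does not oblige anyone to stop dosing healthy contacts while the DSMB considers it. And a related SAE reported on, say, day 10 reaches the sponsor within a day of notification but reaches the DSMB only if the investigator chooses to consult it. Either event would have paused phase 2.

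**Working it through.** **1. Is there a phase 3 trigger anywhere?** Taking each candidate provision in turn:

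| Provision | What it supplies for phase 3 |
|---|---|
| Section 8, six criteria | Tied to phase 2 enrolment |
| Section 7.2.3, pointer to section 8 | Sits in the sentence on DSMB review of phase 2 |
| Section 4.5.2 | Withdrawal of an individual from the intervention |
| Section 4.5.5 | Who is told of a suspension, not what causes one |
| Section 9.3.3 | Interim analysis of PEP effects; no safety trigger |
| Section 12.2 | Permission to act at once; no event named |
| SAP section 3.1.1 | Phase 2 only |

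None names a phase 3 event that requires a pause.

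**2. Does DSMB review cover the 30-day recording window?** Both statements of the phase 3 role refer to active follow-up. Section 7.2.3 makes phase 3 monitoring active at the safety visit and spontaneous afterwards. Events reported from then to day 30 are recorded but fall outside the wording of the DSMB's task. The as-needed consultation remains; it is discretionary and concerns single events.

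**3. What could phase 2 rule out?** Inputs: 150 per arm, about 75 of them minors (section 4.3), and 44 healthy recipients of a single 800 mg dose (Annex 1). With zero events in n, the one-sided 95% upper limit is 1 − 0.05^(1/n).
- n = 150: 1.98%, about 1 in 51.
- n = 75: 3.92%, about 1 in 26.
- n = 150 + 44 = 194: 1.53%, about 1 in 65. This assumes no related SAE among the 44; the annex reports only the absence of large QTc values or changes and of ECG-related events.

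**4. Scale of phase 3.** Section 4.3 gives 22 clusters per arm and 1,708 analysable people per cluster. 44 × 1,708 = 75,152 reproduces the protocol's total, and 22 × 1,708 = 37,576 is the BE-PEP arm. The documents give no SAE risk, so the risks below are illustrative.

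| Assumed risk p | Chance phase 2 sees at least one, 1 − (1 − p)^150 | Expected in phase 3, 37,576p |
|---|---|---|
| 1 in 1,000 | 13.9% | 37.6 |
| 1 in 2,000 | 7.2% | 18.8 |
| 1 in 5,000 | 3.0% | 7.5 |
| 1 in 10,000 | 1.5% | 3.8 |

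**5. Coincidental events.** Counting one 30-day window per person, 37,576 × 30/365 is about 3,090 person-years. The documents give no mortality rate; at an assumed 2 to 8 deaths per 1,000 per year, 6 to 25 deaths would fall in the window by chance (3,090 × 0.002 = 6.2; 3,090 × 0.008 = 24.7). Each needs a relatedness judgement, so the last column of step 4 does not forecast DSMB workload.

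**6. Dosing windows in Table 3.** A repeat dose is due on days 23 to 37 (30 ± 7). A contact due on day 30 misses it if a pause exceeds 37 − 30 = 7 days; one whose window has just opened misses it if the pause exceeds 37 − 23 = 14 days. First doses are due 30 ± 30 days after the last person in the village is screened, so a pause can affect them too.

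**The case against.** The strongest reply is that phase 3 is not unsupervised. It starts only after DSMB, ethics and regulatory clearance. It has a safety visit after each dose, 24-hour SAE reporting, yearly listings to two ethics bodies and a standing DSMB, and the sponsor may suspend or make safety changes at once. All of this stands. A reader might infer from section 8 that phase 3 lacks safety oversight; the documents do not support that.

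A reader might also infer that the DSMB has no part in events reported after the safety visit. That goes too far: the as-needed consultation in section 7.2.3 covers any (S)AE. What is missing is a required review.

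Nor should the lack of a DSMB meeting schedule be held against the protocol. The annexed advice itself sends committee meetings to a charter, and no DSMB charter was supplied. That charter or the SAE SOP may also hold triggers; if so, a cross-reference would be enough.

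Existing data are reassuring. The 44 healthy recipients of 800 mg had no QTc above 500 ms, MDR-TB use spans a decade, paediatric dosing data exist, and section 7.1.3 predicts a worst-case M2 peak below 130 ng/mL after two doses, against 361 ng/mL at steady state in MDR-TB treatment. This lowers the likely risk but says little about rare events. The documents report no clinical safety data on two 800 mg doses given with rifampicin to healthy people.

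Finally, the phase 2 criteria do not transfer unchanged. Phase 3 measures no ECG or liver enzymes. Its relatedness scale has two levels, and the upper one takes in any event with a potential link, with listed symptoms such as syncope classed as related if they occur within 24 hours. A pause rule on that scale could fire on coincidence. This stands, and it shapes the fix.

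**Conclusion.** The point holds as a gap in protocol-level rules. All six pause criteria apply to phase 2, no phase 3 event requires a pause, and events reported between the safety visit and day 30 have no required DSMB review. This is a stated scope that gives phase 3 weaker protection than phase 2, and it leaves the annexed advice on phase 3 stopping criteria unmet in the protocol text.

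Severity is minor to moderate. The textual finding needs no assumption beyond the documents supplied. The expected SAE counts rest on assumed risks, on the planned 83% uptake and on the blanket coverage that section 9.3.1 assumes. They show that phase 2 cannot exclude risks that would matter at phase 3 scale; they are not evidence that BE-PEP is unsafe.

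**What to change.** Add to section 8, for phase 3:

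1. **Main change.** Every SAE within 30 days of any dose that a study physician judges related, whether found at the safety visit or reported spontaneously, goes promptly to the DSMB with arm and dose number. The DSMB decides whether dosing pauses.
2. **Related death.** A death that a study physician judges related to study drug pauses first and repeat BE-PEP dosing until the DSMB decides. The rule should name dosing, because clusters are already randomized by then.
3. **Doses missed through a pause.** Omit and record repeat doses that pass D0 + 30 (± 7), and keep those contacts in arm 1 for analysis. For first doses that pass the 30 (± 30) day window, either deliver them late after the pause or offer them in the next round. The latter needs an exception to the section 4.2 remark that people missed in one round are not automatically included the next year.

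Leave out the ECG and laboratory criteria. A separate Grade 4 clinical trigger is unnecessary, because Grade 4 means life-threatening and such an event is already an SAE. Align the SAE SOP and DSMB charter, or cross-refer if they already say this.

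The direct cost is wording and a tabulation by arm and dose number, with no new committee, visit or test. There will also be an unknown number of DSMB referrals, some of them coincidental. The real downside is that a pause acts on arm 1 only. It could delay or remove first and repeat doses there, and section 9.3.1 excludes people who did not receive PEP, so a long pause would change who enters the primary analysis. That is why item 3 belongs in the same amendment.
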